1.3 SCHEDULE OF ACTIVITIES (SOA)

Procedures	Screening	Baseline	Ketamine Infusions	24 hour Follow-Up Visit	Assessment of Response to Ketamine	WET Sessions	Weekly Assessment Until 12 weeks	Monthly Assessment Until Loss-of-Response
	Day - 28 to 0	Visit 1a, Day 1	Visit 1a-9; Days 1, 3, 5, 8, 11, 12	Visit 1b, Day 2	Visit 5, Day 9	Visit 6-12, Days 10, 12, 16, 18, 22	Visits 10, 13-23, Days 12, 19, 26...	Visits 23-26, Days 33...
Informed consent	x							
Demographics	x							
Medical history	x							
SCID-5	x							
CAPS-5	x	x			x		x	x
MADRS	x	x			x		x	x
WTAR	x							
MoCA	x							
IES-R		x	x	x	x			
QIDS-SR		x	x	x	x			
PCL-5	x	x			x		x	x
MOS-5		x					x ¹	
CES		x					x ¹	
PACT		x					x ¹	
CTQ	x							
TLEQ	x							
SDS	x	x		x	x		x	x
HMS			x ²					
PIQ			x ²					
C-SSRS	x	x			x		x	x
CADSS		x	x					
BPRS		x	x					
YMRS		x	x					
Extinction Learning Task	x				x			
CGI	x	x	x	x	x		x	x
Concomitant medication review	x	x	x	x	x		x	x
PRISE	x	x	x	x	x		x	x

Adverse event review and evaluation	x	x	x	x	x	x	x	x
Physical exam (including height and weight)	x							
Vital signs	x		x					
Weight	x		x					
EKG	x							
Routine labs	x							
Plasma ketamine and norketamine levels			x ³					
Urine pregnancy test	x		x					
Urine drug screen (UTOX)	x		x					
Ketamine infusion (0.5 mg/kg)			x					
Written Exposure Therapy (WET)						x		
Complete Case Report Forms (CRFs)	x	x	x	x	x	x	x	x

¹Visit 14 and 23 only

²only at Infusions 1 and 2

³only at Infusion 1

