2.3 RISK/BENEFIT ASSESSMENT

2.3.1 KNOWN POTENTIAL RISKS

Risks to privacy and confidentiality:

As the research study involves collection of protected and sensitive health information, there is a potential risk of loss of confidentiality. This risk will be conveyed to subjects as part of informed consent and will be minimized by using Standard Operating Procedures at our Depression and Anxiety Center, which comply with Health Insurance Portability and Accountability Act rules.

Risks associated with blood draw or insertion of intravenous canula:

Subjects might feel pain during blood draw or when IV is inserted, and can develop bruising, and rarely, infection. The sight of blood or insertion of IV canula may also cause dizziness or brief loss of consciousness due to vasovagal response. Therefore, all blood draws will be conducted by trained personnel, using aseptic precautions, and in a setting where the subject is resting comfortably and the risk of fall is minimized.

Risks associated with psychological questionnaires and assessments:

Answering questions related to mental health and past experiences may be stressful. Research interviews will be interrupted if subjects become distressed or object to answering questions. If in the judgment of the PI or study-affiliated psychiatrist, the patient has worsened to such a degree that further participation would put the patient at risk, then the subject will be discontinued from the study and provided appropriate clinical care.

Risks associated with ketamine infusion:

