Secondary outcome measures (exploratory): The CAPS-5 will be administered weekly (beginning at baseline prior to the first ketamine infusion) until 6 weeks from the start of WET; thereafter, the CAPS-5 will be administered weekly as tolerated until 12 weeks; all participants will be administered the CAPS-5 at the 12-week time point. Participants who maintain PTSD symptom improvement after 12 weeks will be assessed monthly up to 24 weeks from the start of WET or until loss of improvement, by the blinded clinical rater. The PCL-5 and SDS (self-report scales), the MADRS (administered by the blinded clinical rater), and the CGI-S and CGI-Improvement scales (administered by a study psychiatrist or clinician) will be administered at the same time points until 12 weeks, and then monthly up to 24 weeks or until loss of improvement (See **3.1 Schedule of Activities**). The Quick Inventory of Depressive Symptomatology-Self-Report version (QIDS-SR)⁶⁶ and the Impact of Events Scale-Revised (IES-R),⁶⁷ both self-report scales, will be administered at baseline, 24 hours after the first infusion, at each infusion visit, and on the day of response to ketamine assessment, to capture any ketamine-related rapid changes in symptom levels. An abbreviated version of the Medical Outcomes Study Social Support Survey (MOS-SSS),⁶⁸ the Centrality of Event Scale (CES),⁶⁹ and the Perceived Ability to Cope with Trauma Scale (PACT)⁷⁰ will be administered at baseline (prior to any infusions) and again 3 weeks after the first WET session; data from these scales will be used for Aim-3 analyses.

Safety Assessments: Participants will be evaluated prior to each infusion by the PI or another study-affiliated psychiatrist; including review of vital signs, weight/BMI, drug and pregnancy tests, concomitant medications and adverse events. Participants will be monitored continuously during all ketamine infusions. On infusion days, side effects will be assessed with the Patient-Rated Inventory of Side Effects (PRISE) Adverse Event Visit Checklist,⁷¹ the Clinician-Administered Dissociative States Scale (CADSS),⁷² the Brief Psychiatric Rating Scale (BPRS) 4 items assessing positive symptoms,⁷³ and the Young Mania Rating Scale first item.⁷⁴

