7 STUDY INTERVENTION DISCONTINUATION AND PARTICIPANT DISCONTINUATION/WITHDRAWAL

7.1 DISCONTINUATION OF STUDY INTERVENTION

Discontinuation from ketamine or WET does not mean discontinuation from the study, and remaining study procedures should be completed as indicated by the study protocol. If a clinically significant finding is identified (including, but not limited to changes from baseline) after enrollment, the investigator or qualified designee will determine if any change in participant management is needed. Any new clinically relevant finding will be reported as an adverse event (AE).

The data to be collected at the time of study intervention discontinuation will include the following:

- Symptom measures (e.g.,CAPS-5, MADRS, PCL-5, SDS)
- Global Clinical Severity and Improvement (CGI-S and CGI-I)
- End-Of-Infusion labs
- Safety data
- Concomitant medications
- Follow-up plan

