7.2 PARTICIPANT DISCONTINUATION/WITHDRAWAL FROM THE STUDY

Participants are free to withdraw from participation in the study at any time upon request.

An investigator may discontinue or withdraw a participant from the study for the following reasons:

- Pregnancy
- Significant study intervention non-compliance
- If any clinical adverse event (AE), laboratory abnormality, or other medical condition or situation occurs such that continued participation in the study would not be in the best interest of the participant
- Disease progression which requires discontinuation of the study intervention
- If the participant meets an exclusion criterion (either newly developed or not previously recognized) that precludes further study participation
- Participant unable to receive a total of four or six ketamine infusions, or unable to participate in WET.

The reason for participant discontinuation or withdrawal from the study will be recorded on the Visit Check-list Case Report Form (CRF). Subjects who sign the informed consent form and begin study procedures but do not receive the study intervention may be replaced. Subjects who sign the informed consent form, and begin study procedures and receive the study intervention, and subsequently withdraw, or are withdrawn or discontinued from the study, will not be replaced.

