The **Columbia Suicide Severity Rating Scale (C-SSRS)** is a comprehensive, semi-structured interview measure commonly employed in clinical trials. The C-SSRS measures the full spectrum of suicidality, including passive and active suicidal ideation, suicidal intent, and suicidal behaviors.⁶⁰ All study subjects will be assessed for suicidal ideation and behavior by the study PI or other trained member of the study team. Both past-month and lifetime versions of the C-SSRS will be administered at study screening. Individuals who score a 4 or greater on the past-month suicidal section, or who have engaged in any suicidal behavior in the past month, will be excluded and referred promptly for clinical care. Our clinicians and staff at the Depress Anxiety Center all undergo formal web-based training on administering the C-SSRS, and have extensive experience in its utilization. The Center has established SOPs for handling suicidality. For patients who do not show suicidality at the described threshold and proceed to participate in this study, the C-SSRS will be administered at each assessment time point (until 12 weeks, and then monthly up to 24 weeks or until loss of response), to assess for suicidal ideation and participant safety throughout the study. Participants with scores of 4 or greater at any point during the study will be exited from the study and promptly referred for clinical care.

The **Sheehan Disability Scale (SDS)** is a brief, 5-item self-report scale that assesses functional impairment in domains of work or school, social life, and family life.⁵⁹ Higher scores on this scale represent higher functional impairment. This scale will be administered at screening, and then at each assessment time point (weekly until 12 weeks, and then monthly up to 24 weeks or until loss of response).

The **Clinical Global Impression –Severity and –Improvement scales (CGI-S and CGI-I)** are among the most widely used brief assessment tools in psychiatry and clinical trials.⁸² The CGI-S will be administered

at screening and baseline prior to any infusions, and both the CGI-S and the CGI-I will be administered at each assessment time point (weekly until 12 weeks, and then monthly up to 24 weeks or until loss of response) by the PI or another study clinician, to determine global severity of psychiatric illness.

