8.3.9 REPORTING OF PREGNANCY

In the event that a participant becomes pregnant while completing the study intervention(s), the participant will be exited from the trial after having completed end-of-infusion safety labs. Any pregnancies that occur while a subject is active in the protocol and after they have received ketamine infusions will be reported to the DSMB, ISMMS IRB, and other agencies (FDA, OHRP) as necessary.

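### Read literally, the mandatory study exit at a C-SSRS score of 4 or more loses the week-12 primary CAPS-5 for a reason tied to clinical state, and conflicts with the plan to assess everyone at week 12

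*Combined protocol and SAP*

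**What the plan says.** Section 8.1 (C-SSRS paragraph) sets the rule: "Participants with scores of 4 or greater at any point during the study will be exited from the study". Referral for clinical care follows. The scale is given at each assessment time point to week 12 and then monthly to week 24. The same threshold, over the past month, excludes people at screening (sections 2.3.3 and 8.1).

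The Schedule of Activities (section 1.3) lists the WET sessions as "Visit 6-12, Days 10, 12, 16, 18, 22" and the last infusion on Day 12.

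On the week-12 assessment, section 4.1 says "all participants will be administered the CAPS-5 at the 12-week time point". Section 4.4 makes that visit the earliest end of study for everyone, and section 9.4.3 also promises it for all.

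On stopping treatment, section 7.1 says: "Discontinuation from ketamine or WET does not mean discontinuation from the study, and remaining study procedures should be completed".

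Other safety withdrawals exist. Section 2.3.1 has one that starts "If in the judgment of the PI or study-affiliated psychiatrist, the patient has worsened to such a degree", and section 7.2 opens its list with "An investigator may discontinue or withdraw a participant from the study for the following reasons". Both leave room for judgment. Pregnancy during the intervention is mandatory: "the participant will be exited from the trial after having completed end-of-infusion safety labs" (section 8.3.9). Under section 7.2, treated participants who withdraw, or "are withdrawn or discontinued from the study, will not be replaced".

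On analysis, section 9.3 defines the ITT set as all enrolled patients and the per-protocol set as those who completed the study. Section 9.4.2 reports the mean CAPS-5 change with a 95% confidence interval and gives no rule for a missing week-12 score.

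**The concern.** The exit is triggered by severe suicidal ideation, so a week-12 score lost through it is unlikely to be missing at random. People in that state have probably improved less on the CAPS-5 than the rest. If so, the mean change among those still observed looks better than the mean for all who were treated, and so does the proportion with at least 30% improvement. The pilot's main product is that one estimate. The synopsis ties further study of the combination to it, and section 9.4.3 foresees a comparison with the completed ketamine trial.

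The loss is harder to justify after Day 22, when the exit stops no study treatment. The rule also leaves site staff with two instructions that cannot both be followed: exit the participant, and assess every participant at week 12.

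**Working it through.** **The plan's own figure.** Section 9.2 states a half-width of 0.5 SD for N = 15. With the normal quantile, 1.960/√15 = 0.506, which reproduces it. (With the t quantile, 2.145/√15 = 0.554.) Losing one score gives 1.960/√14 = 0.524. Precision barely moves, so the issue is bias.

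**Timing.** The weekly column of the schedule covers visit 10 and visits 13 to 23, which is 12 visits. Starting on Day 12 at 7-day steps, the last falls on Day 12 + 11 × 7 = 89. Counting 84 days from the first WET session on Day 10 gives Day 94. Both are long after Day 22.

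- Post-baseline C-SSRS checks before visit 23: Day 9 plus Days 12, 19, …, 82, that is 1 + 11 = 12.
- Of these, after Day 22: Days 26, 33, …, 82, up to 9.
- Of those 9, in the required weekly period to week 6: Days 26, 33, 40 and 47, so 4. The rest are as tolerated.

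These counts show when the rule can act. They do not show how often it will.

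**Shift in the mean.** Let k participants exit without a week-12 score, and let each have improved D points less than the mean M of the others. The full mean improvement is [(15 − k)M + k(M − D)]/15 = M − kD/15, so the observed mean is too high by kD/15. D is not in the documents; I assume 10 to 20 points.

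- k = 1, D = 10: 10/15 = 0.67 points.
- k = 1, D = 20: 20/15 = 1.33 points.

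For scale, section 4.2 reports a difference of 11.88 points and d = 1.13 for the completed ketamine trial, so SD = 11.88/1.13 = 10.51. This comes from a two-week between-group contrast and is assumed to apply to 12-week change. Half of it is 5.26 points, so one exit shifts the mean by 0.67/5.26 = 13% to 1.33/5.26 = 25% of the planned half-width.

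**Shift in the 30% proportion.** Suppose one exited non-responder drops out of the denominator.

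- With 5 responders: 5/15 = 33.3% becomes 5/14 = 35.7%, up 2.4 points.
- With 9 responders: 9/15 = 60.0% becomes 9/14 = 64.3%, up 4.3 points.

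**Chance of any exit.** No rate is given. For an assumed per-person rate p, the chance of at least one exit among 15 is 1 − (1 − p)^15: 26% at p = 2%, 54% at 5% and 79% at 10%. At p = 0 the effect is nil. None of these is an estimate.

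**The case against.** **It is a deliberate safety rule.** One threshold governs both entry and continuation, and section 7.2 lists a newly met exclusion criterion as a ground for withdrawal. A fixed cut-off for severe ideation is defensible after ketamine and trauma-focused writing. This stands: a reader might infer that the rule is a safety error, and nothing in the documents supports that. The treatment stop and the referral should not be touched.

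**Exit after Day 22 still does something.** It releases the participant from the synopsis request not to change concomitant treatment, and it ends repeated CAPS-5 interviews of about 40 minutes. This also stands. The release can be given without ending assessment, and the interviews can be cut to one at week 12.

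**The loss is inferred.** No section says that the week-12 CAPS-5 is withheld after exit, and sections 4.1, 4.4 and 9.4.3 point the other way. That is correct, so a reader should not take the loss as certain. But the text then contradicts itself and needs reconciling.

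**Much is already captured.** CAPS-5 and C-SSRS share visits, so a CAPS-5 near the time of exit is normally available through week 6. Section 9.4.1 reports counts of non-missing values, section 9.4.3 reports change at each time point and plots individual trajectories, and section 7.2 records withdrawal reasons. Adverse event capture runs on for 7 or 30 days (section 8.3.4). A further rule to report numbers and reasons would therefore add little. None of this supplies the week-12 value, and the mixed model in section 9.4.3 is optional and exploratory.

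**The missing-data gap is general.** Dropout and the judgment-based withdrawals also lack a rule, and some are just as tied to clinical state. This stands, and the analysis rule should cover a missing score from any cause.

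**Post-exit scores can mislead too.** In a single-arm study, a score taken after new treatment may credit rescue care to ketamine plus WET. This stands, and is why both analyses should be shown.

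**Conclusion.** The concern holds in a limited form. Section 8.1 orders exit at any time with no assessment-only follow-up. Read literally, that loses the primary outcome for a reason tied to clinical state, even after study treatment is over. It conflicts with sections 4.1, 4.4 and 9.4.3, and it sits badly with the principle in section 7.1. Only exits before the week-12 visit matter for the primary outcome.

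The likely direction is an over-favourable mean change. This rests on the judgment that people with severe ideation have improved less. The size is unknown and may be nil, because no exit rate is given and screening excludes recent scores of 4 or more. The 0.7 to 1.3 points per exit depend wholly on the assumed deficit, and the 13% to 25% also on a borrowed SD. A reader might infer that the pilot's estimate will be materially biased; the documents do not support that. The analysis is descriptive with up to 15 people, so no test is at risk. This is a cheap improvement worth making.

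**What to change.** **Section 8.1.** Replace the exit with wording such as: *A participant who scores 4 or more receives no further ketamine or WET, is referred promptly for care, and is released from the request not to change concomitant treatment. Unless the participant withdraws consent or the study psychiatrist judges assessment unsafe, the participant remains in the study for safety checks and the week-12 CAPS-5. Any new treatment is recorded.*

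**Section 9.4.2.** Add three rules:

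- Report the mean change with all available week-12 scores.
- As a sensitivity analysis, set the change to zero for participants with no week-12 score and for those whose score follows new treatment after a C-SSRS stop. Zero is not a worst case, since someone may have worsened.
- In the week-12 30% proportion, count anyone without a week-12 score, for any reason, as not improved.

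The judgment-based withdrawals in sections 2.3.1 and 7.2 stay as they are.

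**Cost.** A protocol amendment and a line in the consent form; one extra CAPS-5 and brief safety checks per affected participant. The main downside is that a retained week-12 score may partly reflect rescue care, which the sensitivity analysis shows but does not remove.

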8.2 SAFETY AND OTHER ASSESSMENTS

Participants in this proposed study will provide the following safety data:

- (A) Data related to medical history, physical examination including review of systems, vital signs, ECG, routine laboratory tests (comprehensive metabolic panel, complete blood count, thyroid function testing) needed to determine eligibility and to monitor safety of participants
- (B) Measures to assess for any acute side effects associated with ketamine before and after each infusion; potential longer- lasting side effects will be assessed weekly until resolution.

For laboratory tests, all results will be reviewed by the PI or study-affiliated psychiatrist, and any incidental finding will be conveyed to the subject with provision for additional work-up if needed.

Plasma ketamine and norketamine levels will be assessed via serial blood draws at the first ketamine infusion. Blood will be drawn from a second IV catheter at 30, 60, 90, and 120 minutes from the start of the infusion. Samples will be spun down and aliquoted into plasma samples. These samples will then be transported to Mount Sinai Clinical Laboratory Services (Sinai Labs) for shipment to an external laboratory (LabCorps) for the ketamine and norketamine levels.

The **Patient-Rated Inventory of Side Effects (PRISE)** Adverse Event Visit Checklist⁷¹ is a clinician-administered questionnaire used to qualify side effects by identifying and evaluating the tolerability of each symptom. This scale will be completed before and after each infusion, and at each assessment time point (weekly until 12 weeks, and then monthly up to 24 weeks or until loss of response), by the PI or another study psychiatrist.

8.3 ADVERSE EVENTS AND SERIOUS ADVERSE EVENTS

8.3.1 DEFINITION OF ADVERSE EVENTS (AE)

All adverse events (AEs), defined as any physical or clinical change or disease experienced by a participant at any time during the course of the study, will be recorded in the participant's research records and will be captured in the electronic data capture system. [name] will be responsible for reporting to and following the guidance of any other applicable oversight bodies, including (but not limited to) the Institutional Review Board, the Data Safety and Monitoring Board.

8.3.2 DEFINITION OF SERIOUS ADVERSE EVENTS (SAE)

An adverse event (AE) or suspected adverse reaction is considered "serious" if, in the view of either the investigator or sponsor, it results in any of the following outcomes: death, a life-threatening adverse event, inpatient hospitalization or prolongation of existing hospitalization, a persistent or significant incapacity or substantial disruption of the ability to conduct normal life functions, or a congenital anomaly/birth defect. Important medical events that may not result in death, be life-threatening, or require hospitalization may be considered serious when, based upon appropriate medical judgment, they may jeopardize the participant and may require medical or surgical intervention to prevent one of the outcomes listed in this definition. Examples of such medical events include allergic bronchospasm requiring intensive treatment in an emergency room or at home, blood dyscrasias or convulsions that do not result in inpatient hospitalization, or the development of drug dependency or drug abuse.

8.3.3 CLASSIFICATION OF AN ADVERSE EVENT

8.3.3.1 SEVERITY OF EVENT

For adverse events (AEs) not included in the protocol defined grading system, the following guidelines will be used to describe severity.

- **Mild** – Events require minimal or no treatment and do not interfere with the participant's daily activities.
- **Moderate** – Events result in a low level of inconvenience or concern with the therapeutic measures. Moderate events may cause some interference with functioning.
- **Severe** – Events interrupt a participant's usual daily activity and may require systemic drug therapy or other treatment. Severe events are usually potentially life-threatening or incapacitating. Of note, the term "severe" does not necessarily equate to "serious".

8.3.3.2 RELATIONSHIP TO STUDY INTERVENTION

All adverse events (AEs) must have their relationship to study intervention assessed by the clinician who examines and evaluates the participant based on temporal relationship and his/her clinical judgment. The degree of certainty about causality will be graded using the categories below. In a clinical trial, the study product must always be suspect.

- **Definitely Related** – There is clear evidence to suggest a causal relationship, and other possible contributing factors can be ruled out. The clinical event, including an abnormal laboratory test result, occurs in a plausible time relationship to study intervention administration and cannot be explained by concurrent disease or other drugs or chemicals. The response to withdrawal of the

study intervention (dechallenge) should be clinically plausible. The event must be pharmacologically or phenomenologically definitive, with use of a satisfactory rechallenge procedure if necessary.

- **Probably Related** – There is evidence to suggest a causal relationship, and the influence of other factors is unlikely. The clinical event, including an abnormal laboratory test result, occurs within a reasonable time after administration of the study intervention, is unlikely to be attributed to concurrent disease or other drugs or chemicals, and follows a clinically reasonable response on withdrawal (dechallenge). Rechallenge information is not required to fulfill this definition.
- **Potentially Related** – There is some evidence to suggest a causal relationship (e.g., the event occurred within a reasonable time after administration of the trial medication). However, other factors may have contributed to the event (e.g., the participant's clinical condition, other concomitant events). Although an AE may rate only as "possibly related" soon after discovery, it can be flagged as requiring more information and later be upgraded to "probably related" or "definitely related", as appropriate.
- **Unlikely to be related** – A clinical event, including an abnormal laboratory test result, whose temporal relationship to study intervention administration makes a causal relationship improbable (e.g., the event did not occur within a reasonable time after administration of the study intervention) and in which other drugs or chemicals or underlying disease provides plausible explanations (e.g., the participant's clinical condition, other concomitant treatments).
- **Not Related** – The AE is completely independent of study intervention administration, and/or evidence exists that the event is definitely related to another etiology. There must be an alternative, definitive etiology documented by the clinician.

